9.2.1. Pregnancy

Female subjects of child-bearing potential will have urine pregnancy tests conducted at screening and at any timepoints during the study, if needed. Only subjects with negative pregnancy test results will be enrolled. Any subjects with positive pregnancy test results at any time during the study will be presented in a listing.

9.2.2. Events of Clinical Interest

The frequency and percentage of subjects with the following elevations will be summarized at any post-baseline visit:

- ALT or AST $> 8 \times$ the upper limit of normal (ULN);
- ALT or AST $> 5 \times$ ULN if new compared to Baseline;
- ALT or AST $> 3 \times$ ULN and total bilirubin $> 2 \times$ ULN if new compared to Baseline;
- ALT or AST $> 3 \times$ ULN.

If subjects meet the criterion ALT or AST $> 3 \times$ ULN, the additional summary of the frequency and percentage of subjects with ALT or AST $> 3 \times$ ULN, confirmed by repeat test, and with the appearance of fatigue, nausea, vomiting, right upper quadrant pain or tenderness, fever, rash, and/or eosinophilia ($> 5\%$) will be provided.

A listing will be provided for the above elevations, including the actual measurement of ALT, AST, and total bilirubin, and their reference high limits.

9.3. Vital Sign Measurements

Summary tables will be presented for vital sign data, including systolic blood pressure (mmHg), diastolic blood pressure (mmHg), body temperature ($^{\circ}\text{C}$), respiratory rate (bpm), and pulse rate (bpm), by treatment for subjects in the safety set. Observed results at the scheduled visits and changes from baseline to the TOC visit will be presented. All vital sign data by subject will be presented in a listing.

9.4. Physical Examination

The abbreviated physical examinations will be conducted at Screening and at the TOC visit.

The abbreviated physical examination comprises a routine medical examination including general appearance and an overall examination of body systems.

All abbreviated physical examinations will be classified as Normal, and Abnormal at baseline. For post-baseline examinations will be classified as “Changes from baseline” or “No change from

baseline”. This categorical data will be summarized with the frequency and percentage of subjects by body system at each scheduled visit.

Any abnormalities noted during the physical examination will be presented in a listing for all subjects.

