14.11 Rating of Vulvovaginal Signs by the Investigator Using the VSS Scale

The investigator (or qualified designee) will perform vulvovaginal examinations to rate the subject's signs of infection at the Screening and TOC visits. The vulvovaginal examination will be repeated at the FU visit only if the subject presents symptoms. Otherwise, no additional vulvovaginal examination will be conducted or signs rated. Vulvovaginal examinations may be conducted at unscheduled visits, if needed.

If the subject experiences persistence or worsening or recurrence of symptoms that per the investigator's assessment (e.g. symptoms ≥ 3) warrant the use of rescue antifungal therapy, a

vaginal examination with rating of signs by the investigator should be completed prior to initiation of rescue therapy. If the investigator's rating of the vulvovaginal signs is not possible prior to the initiation of the rescue therapy, it should still be completed as soon as possible after rescue therapy is initiated.

Investigators will assess the signs of infection using the VSS Scale provided in [Section 21.0 \[Appendix B\]](#)), a standardized, predefined scale where each sign of the vagina and/or vulva will be given a numerical rating based on severity, as follows:

- Edema: absent = 0; mild = 1; moderate = 2; severe = 3
- Erythema: absent = 0; mild = 1; moderate = 2; severe = 3
- Excoriation or fissures: absent = 0; mild = 1; moderate = 2; severe = 3

Other findings will be recorded using the most relevant medical term in the abbreviated physical examination page of the eCRF.

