3.2.2. Secondary Efficacy Endpoints

Efficacy as measured by:

- The percentage of subjects with mycological eradication (negative culture for growth of *Candida* species) at the TOC visit;
- The percentage of subjects with clinical cure and mycological eradication (responder outcome) at the TOC visit;

- The percentage of subjects with complete resolution of symptoms at the Follow-up (FU) visit;
- The percentage of subjects with clinical improvement (partial or complete resolution of signs and symptoms with total composite score no greater than 1) at the TOC visit;
- The absolute change in signs and symptoms score from Baseline to TOC and FU visits.

Safety and tolerability as measured by:

- Adverse events (AEs);
- Vital signs;
- Physical examination;
- Treatment discontinuation;
- Safety laboratory tests.

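### The physical-examination table in SAP 9.4 counts improvement and deterioration together as a change from baseline, so it cannot show new or worsened abnormalities by arm

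*SAP*

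**What the plan says.** SAP 3.2.2 introduces five measures with "Safety and tolerability as measured by", and physical examination is one of them. Protocol 9.2 lists it too. Protocol 18.7.2 describes no analysis of it, so SAP 9.4 is the only specification.

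SAP 9.4 sets these rules:

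- Content: "The abbreviated physical examination comprises a routine medical examination including general appearance and an overall examination of body systems".
- Baseline: "All abbreviated physical examinations will be classified as Normal, and Abnormal at baseline".
- After baseline: "For post-baseline examinations will be classified as “Changes from baseline” or “No change from" (the sentence ends with the word baseline).
- Display: "This categorical data will be summarized with the frequency and percentage of subjects by body system at each scheduled visit".
- Listing: "Any abnormalities noted during the physical examination will be presented in a listing for all subjects".

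The examination takes place at Screening and TOC (Protocol 14.5 and Table 1), so TOC is the only scheduled examination after baseline.

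Protocol 14.11 governs which vulvovaginal findings reach this page. Edema, erythema and excoriation or fissures go on the VSS Scale: "Investigators will assess the signs of infection using the VSS Scale provided in" Appendix B. For anything else seen at that examination: "Other findings will be recorded using the most relevant medical term in the abbreviated physical examination page of the eCRF".

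**The concern.** A safety table should let the reader compare how many subjects in each arm developed something new or got worse. With only a change/no-change split, a finding that went away counts the same as one that appeared. This affects every body system, whatever the disease under study.

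The disease adds a second route. Every woman enters with symptomatic infection, and Protocol 14.11 directs unscored vulvovaginal findings to this page. If such findings are recorded at Screening and clear with treatment, the clearance is counted in a safety table. A difference between arms could then reflect benefit, harm or both, and the table would not say which.

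**Working it through.** The plan states no figure for this table, so there is none to reproduce. The check has three parts.

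**1. What the two categories can separate.** For one body system, the possible paths from baseline to TOC are:

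| Baseline | TOC | SAP 9.4 category |
|---|---|---|
| Normal | Normal | No change |
| Normal | Abnormal | Change |
| Abnormal | Normal | Change |
| Abnormal | Abnormal, same | No change |
| Abnormal | Abnormal, better or worse | Change |

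The baseline row gives the share b abnormal at Screening, and the TOC row gives the share c changed. Because the two are not crossed, the share going from normal to abnormal is known only to lie between max(0, c − b) and min(c, 1 − b). For example, with b = 10% and c = 5% (assumed values), it lies anywhere from 0% to 5%. All of the changes could be new abnormalities, or none of them.

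**2. How the SAP treats its other safety data.**

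| Data | Section | Direction kept? |
|---|---|---|
| Laboratory tests | SAP 9.2 | Yes: low/normal/high shift from baseline to TOC |
| Vital signs | SAP 9.3, with the change formula in SAP 4 | Yes: signed change from baseline |
| Adverse events | SAP 9.1 | Yes: new, or worse than before exposure |
| Physical examination | SAP 9.4 | No |

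**3. How far resolving infection could shift the table.** Inputs:

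- q: share of women with an unscored infection-related finding on the examination page at baseline. The documents do not give it, so the full range is shown.
- r: share of those findings resolved by TOC. Assumed equal to the planned clinical cure rates of 50% and 30% (Protocol 18.1, SAP 4.1).
- m: share of the other women with a new abnormality. Assumed equal in the two arms.

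Expected share with a change = q × r + (1 − q) × m.

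Difference between arms = q × (0.50 − 0.30) = 0.20 × q. The m term cancels.

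| q | Ibrexafungerp, m = 0 | Placebo, m = 0 | Difference (points) |
|---|---|---|---|
| 0% | 0% | 0% | 0 |
| 5% | 2.5% | 1.5% | 1 |
| 10% | 5% | 3% | 2 |
| 25% | 12.5% | 7.5% | 5 |
| 50% | 25% | 15% | 10 |
| 100% | 50% | 30% | 20 |

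With m = 2% and q = 10%, the shares are 0.10 × 0.50 + 0.90 × 0.02 = 6.8% and 0.10 × 0.30 + 0.90 × 0.02 = 4.8%. The difference is again 2 points.

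**The case against.** A reader might infer that the table will show more changes in the more effective arm. The documents do not support that:

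- The three signs that enter clinical cure are rated on the VSS Scale, and the visit schedule lists that rating separately from the abbreviated physical examination.
- Only other findings reach the examination page. Exclusion criterion 1 narrows these further by removing women with another vaginal condition that may interfere with diagnosis or evaluation of response.
- No genital body system is named, and the eCRF page and table shells are not available to check.
- The 50% and 30% are planned rates for clearing all six scored items without further antifungal treatment. They are not resolution rates for some other finding.

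So q may be near zero, and the text supports only that such findings could enter.

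A reader might also infer that harm would be hidden from the safety analysis. That does not follow either. Protocol 16.1 counts an unfavorable and unintended sign as an adverse event. SAP 9.1 restricts the adverse-event summaries to events that are new or worse after exposure, and SAP 9.1.1 to 9.1.3 tabulate them by treatment, relationship and severity. An untoward new examination finding is therefore compared by arm there, and a resolved one is not counted. SAP 9 describes the safety analyses as generally descriptive, no test is planned on this table, and abnormalities are listed by subject. SAP 4 sorts listings by treatment group, so a count by hand is possible.

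These points limit the consequence but do not repair the table. A listing gives no count or percentage of new abnormalities by arm, and the first part of the check holds in every body system even at q = 0.

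**Conclusion.** The concern holds as a low-severity defect in one descriptive table. That SAP 9.4 merges resolution or improvement with new or worsened abnormality follows from its wording and needs no assumption.

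Any tilt toward ibrexafungerp is conditional. It is 20 × q percentage points, from 0 to 20, and rests on three assumptions: unscored infection-related findings are recorded at baseline, they resolve at the planned cure rates, and new abnormalities are equally frequent in both arms. Since q is not given, no narrower range can be defended. The effect is confined to this table; it leaves the efficacy analyses and the adverse-event tables unchanged.

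**What to change.** In SAP 9.4, tabulate TOC examination findings by body system and arm in three categories: new or worsened, no change, resolved or improved. Use the first as the safety result. If normal/abnormal status is recorded at TOC, a baseline-by-TOC shift table is a simpler alternative and matches SAP 9.2, although it would not show worsening within an abnormal examination. State also that signs scored on the VSS Scale are excluded from this table.

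The cost is SAP wording and one revised table shell. The small downside is that recorded findings must be classed by direction, under blind, before database lock. No visit, procedure or clinical rule is affected.

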9.5. Vaginal Samples – pH, KOH and Other Pathogen Results

Vaginal samples will be obtained for pH testing, KOH testing, fungal culture, and other pathogens (Chlamydia, Gonorrhea, and Herpes) at the screening visit and other times during the study when persistence or recurrence of vulvovaginal symptoms occurs. Subjects with other pathogens other than Candida, suspected at screening will be excluded from the study.

The pH testing results will be summarized descriptively at the scheduled post-baseline visits by treatment group.

The KOH testing results will be classified as Positive (Yeast Only), Positive (Yeast and other pathogens), Negative (Yeast and other pathogens), and Positive (Other pathogens only). This categorical data will be summarized with the frequency and percentage of subjects at the scheduled post-baseline visits by treatment group.

The proportion of subjects with Chlamydia, Gonorrhea, and Herpes will be summarized at the scheduled visits by treatment group.

All by-subject vaginal sample testing data will be presented in a listing.

10. Interim Analysis

No interim analysis is planned for this study.

11. Changes in the Planned Analysis

The following have changed from the protocol:

- For the secondary efficacy endpoint “Change from Baseline in Composite Score of the Vulvovaginal Signs and Symptoms” described in Section 8.2.5, an analysis of covariance (ANCOVA) model is recommended rather than a two-way ANOVA model. Baseline value will be considered as possible contributor to any observed differences. Additionally, other variables may be considered during blinded data review.
- Add the randomization stratification factor, diabetes mellitus diagnosis (Yes or No), as justification factor in the efficacy analyses models.

12. References

Sobel, JD. Vaginal candidosis. *Lancet* 2007; 369:1961–71.

William G. Cochran (December 1954). "Some Methods for Strengthening the Common χ^2 Tests". *Biometrics*. 10 (4): 417–451.

Gelman, Andrew (February 2005). "Analysis of variance? why it is more important than ever". *The Annals of Statistics*. 33 (1): 1–53.

13. Appendices

Appendix 1: Schedule of Assessments

Visit	V1 Screening ^a	V2 Baseline ^a	V3 TOC	V4 Follow-up	Unscheduled Visits
Day (allowable window)	D-1 (-2)	D1	D11 (± 3)	D25 (± 4)	
Study Procedures					
Informed consent ^b	X				
Assignment of Subject ID number	X				
Inclusion/exclusion criteria	X	X			
Medical history and demographics	X				
Abbreviated physical exam	X		X		If needed
Urine pregnancy test ^c	X				If needed
Safety labs ^d	X		X		If needed
Rating of vulvovaginal symptoms by the subject ^e	X	X-----X		X	If needed
Vulvovaginal sample for other pathogens and pH ^e	X		If symptoms	If symptoms	If needed
Vulvovaginal sample for KOH ^e	X		If symptoms	If symptoms	If needed
Vulvovaginal sample for fungal culture ^e	X		X	If symptoms	If needed
Rating of vulvovaginal signs by the investigator ^e	X		X	If symptoms ^f	If needed
Randomization		X			
Study drug and subject diary ^g dispensing		X			
Study drug dosing ^h		X			
Subject diary completion		X-----X			
Study drug collection and treatment compliance evaluation			X		

Visit	V1 Screening ^a	V2 Baseline ^a	V3 TOC	V4 Follow-up	Unscheduled Visits
Day (allowable window)	D-1 (-2)	D1	D11 (± 3)	D25 (± 4)	
Study Procedures					
Subject diary collection and review			X		
Vital Signs	X		X		If needed
Prior & concomitant medication review	X	X	X	X	X
AE monitoring	X	X	X	X	X

Abbreviations: AE=adverse event; D=day; TOC=test of cure; V=visit

- a. Screening and Baseline may occur on the same day.
- b. For subjects under the legal age of consent, the subject's parent or legal representative will also sign the subject's ICF.
- c. Results should be reviewed prior to randomization at Baseline (Day 1).
- d. Hematology and blood chemistry. Safety laboratory tests will be performed by a qualified central laboratory.
- e. If the subject experiences persistence or worsening or recurrence of symptoms, after the baseline visit, that per the investigator's assessment (e.g. symptoms ≥ 3) warrant the use of rescue antifungal therapy, the symptoms that led to the use of rescue antifungal therapy must be documented in the eCRF and a vaginal examination with rating of signs by the investigator should be completed. Additionally, vulvovaginal samples should be obtained for KOH testing and pH measurement (both at the site), fungal culture (central laboratory) and investigation of other pathogens such as bacterial vaginosis and *Trichomonas vaginalis* (at the site). If the investigator's rating of the vulvovaginal signs and vaginal samples collection are not possible prior to the initiation of the rescue therapy, they should still be completed as soon as possible after rescue therapy is initiated.
- f. Vulvovaginal examinations will be repeated at the FU visit only if the subject presents symptoms. Otherwise, no additional vulvovaginal examination will be conducted or signs rated.
- g. Subject diaries will be used to rate vulvovaginal symptoms of infection and record study drug dosing details, AEs and concomitant medication use.
- h. If administering the first dose at the study center would complicate the administration of the second dose 12 hours later (e.g. first dose at 3 p.m. will require second dose at 3 a.m.), the subject can self-administer both doses at home to allow for a more convenient dosing schedule (e.g., 8 p.m. and 8 a.m.). Subjects will record study drug dosing details in their study diary
